6.2.5 Sensitivity Analyses for Primary Endpoint

Sensitivity analyses for IPTW stabilized weights

A plot of the distribution of IPTW stabilized weights by group will be used to identify very large weights, and to assess the degree of overlap of the PS distributions of the treatment and control groups.

PS scores close to 0 (for larotrectinib) or 1 (for historical control) may be problematic for IPTW due to the large weights assigned to these observations. Extreme PS values may also signal a lack of comparability between the treatment groups, as these patients may lack a match in the other group. Therefore, trimming at 5% level will be considered, which amounts to dropping the individuals with the most extreme PS values in both groups. Essentially, trimming aims to exclude patients who fall well outside the region of overlap in the PS distributions of the two treatment groups. The minimum PS threshold is set as the value of the 2.5th percentile observed among larotrectinib patients, and the maximum PS threshold is set as the value of the 97.5th percentile observed among historical control patients. All patients who have a PS score outside the window defined by these 5% thresholds will be excluded from this sensitivity analysis. The objective of this sensitivity analysis is to remove 'outlier' patients.

A second sensitivity analysis will apply weight truncation that reduces any 'large' weight down to a maximum weight. Following Elze *et al* [8], we set the weight threshold to 10.

In summary, in addition to the main analyses, the following sensitivity analyses will also be considered:

- a. IPTW (5% trimming)
- b. IPTW (truncating large weights)

A consistency in the findings regarding the treatment effect between the main analysis and the sensitivity analyses should instill confidence in the primary results.

Sensitivity analyses – exact matching

The primary endpoint analysis is expected to provide a rather conservative estimate of the treatment effect. The index date for the patients in the external cohort(s) will correspond to first line of treatment, while for SCOUT patients, the index date will correspond to the second line of treatment for the majority of patients.

To balance the two groups, the following sensitivity analyses will be conducted:

Exact Matching sensitivity analysis

- Exact matching will be applied by the Larotrectinib LOT (line of therapy) by 1st line and $\geq 2^{\text{nd}}$ line. In this matching 2nd line or higher will be lumped together due to smaller number of patients in the control cohort had 3 or more therapies.
- Propensity scores will be generated after identifying matched external control patients to Larotrectinib patients
- The propensity scores will be obtained from a logistic regression model with the dependent variable: Larotrectinib group (yes, no). Key covariates will include: IRS

group, age, and time from locally advanced/metastatic disease diagnosis to initiation of treatment

- The predicted probabilities of receiving Larotrectinib from this logistic regression will form the propensity scores for each patient
- The weight assigned to each patient will be the inverse probability of being in a certain group conditional on the key covariates. For Larotrectinib patients, this is the reciprocal of the propensity score. For the external controls, this is the reciprocal of 1 minus the propensity score.
- These weights will be stabilized by multiplying by the marginal probability of treatment that actually received and will be referred to as the stabilized IPT weights.
- For both weighted and unweighted samples, the primary endpoint will be evaluated using unstratified and stratified log-rank test, where the stratification factor is the LOT (1L, $>=2L$)
- The hazard ratio (Larotrectinib/control) will be computed using a weighted Cox proportional hazards model, regressing survival time on an indicator variable denoting treatment group (Larotrectinib, external controls), stratification factor (1L, $>=2L$), and incorporating the stabilized IPTW weights.
- The index date for the Larotrectinib group is the date of first dose of Larotrectinib administration
- The index date for the external controls is the date of initiation of the matched line of therapy (index therapy)

Subgroup treated with second line of treatment in both groups.

Only those patients who are treated with larotrectinib as second-line treatment (for SCOUT) or take a second line of systemic therapy (for external historical cohorts) will be included in the analysis. The index date is defined as the second line of treatment in both the treatment and control groups. This analysis reflects the current reimbursement scope of larotrectinib, i.e. in patients who are refractory or in relapse.

Subgroup treated with first line of treatment

A similar subgroup analysis will be conducted for comparing first line Larotrectinib patients versus external controls taking at least 1 line of therapy.

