9.7.6 Sensitivity analysis

As the choice of index date and statistical method may affect the results, the following sensitivity analysis will be conducted in order to explore the impact of methodological choices on the results. A consistency in the findings regarding the treatment effect between the main analysis and the sensitivity

analyses should instil confidence in the primary results. Inconsistencies in the results will be explored through further analysis. Further details will be described in the SAP.

- Choice of index date:

As the majority of larotrectinib patients will be receiving 2nd line therapy, this analysis attempts to maximize consistency between treatment groups in terms of line of therapy while committing to the inclusion of all available patients. For SCOUT patients, the index date will be defined as the start date of larotrectinib, regardless of line of therapy. In the external historical control cohort(s), the index date will represent start of chemotherapy. However, control patients who take a second line of therapy will have their index date set at the start of second line, in order to provide a close comparison with the larotrectinib group prior to any adjustment using IPTW. A caveat of this analysis is that it may fail to capture some clinically relevant events, for example control subjects receiving a second line of treatment.

- Subgroup analysis:

For the patients treated with a second line or more of systemic therapies, the index date will be defined as the second line of treatment in both the treatment and control groups.

This analysis will reflect the current reimbursement scope of larotrectinib, i.e. in patients who are refractory or in relapse.

- Statistical method:

A plot of the distribution of IPTW weights by group will be used to identify very large weights. Trimming at 5% level will be considered, which amounts to dropping the individuals with the most extreme PS values in both the treatment and control groups, as they may lack a match in the other group. Weight truncation will also be explored that reduces any 'large' weight down to a maximum weight. Therefore, in addition to the main analyses, the following sensitivity analyses will also be considered:

- a. IPTW (5% trimming)
- b. IPTW (truncating large weights)

A consistency in the findings regarding the treatment effect between the main analysis and the sensitivity analyses should instil confidence in the primary results.

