5.1 Assignment of Analysis Sets

FAS

A patient will be included in the FAS if the patient has taken at least one dose of larotrectinib for SCOUT study, or has fulfilled the eligibility criteria for inclusion into the pooled external cohorts and has initiated chemotherapy.

All analyses detailed below will be repeated separately for two populations of FAS:

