6.7 Additional Analyses Planned to be Reported Outside the Study Report

Not applicable.

7. Document History and Changes in the Planned Statistical Analysis

The complementary analysis on patients with IFS or other STS with *NTRK* gene fusion will no longer take place as there is only one STS patient in the Curie Database and none in the CWS. In its place, analyses will be performed on the population of patients with IFS having documented *NTRK* gene fusion.

The protocol described a sensitivity analysis on choice of index date of the primary endpoint, for subjects in either arm who are treated with a second line or more of systemic therapy or larotrectinib. The index date was specified as the start of second line in both groups. However, as shown below in 2, fewer control subjects received a second line than anticipated, and a larger number of subjects in SCOUT took larotrectinib as the secondline therapy. Therefore, the analysis would have had an unbalanced sample size at N=32 versus 8. In addition, 14 of the 32 larotrectinib subjects start at line 3 to 6, leading to a conservative analysis that unduly favors the control group.

In order to provide a more balanced analysis, we propose to replace this sensitivity analysis for the choice of index date with the sensitivity analysis based on exact matching on the line of therapies, approach as detailed in Section 6.2.5. A subgroup analysis was planned in those treated with second line of treatment in both groups. A similar subgroup analysis will be conducted when comparing first line Larotrectinib patients versus external controls taking at least 1 line of therapy, which was added to Section 6.2.5.

Table2 Line of Therapy

	Larotrectinib	Control
1st Line	19 (37%)	34 (81%)
2nd Line or Higher	32 (63%)	8 (19%)

8. References

- [1] Rosner B. (2006). *Fundamentals of Biostatistics*. (6-th edition). Thomson Brooks/Cole.

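### The exact-matching analysis has no rule for controls with more than one line; if they are sorted as in SAP Table 2, first-line controls are selected on not having had an endpoint event.

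*SAP*

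**What the plan says.** The exact-matching analysis in SAP 6.2.5 has two classes of line. Later lines are pooled: "2nd line or higher will be lumped together due to smaller number of patients in the control cohort had 3 or more therapies". Matched controls are identified before the propensity score is fitted, and the clock is set as follows: "The index date for the external controls is the date of initiation of the matched line of therapy (index therapy". The Cox model is then weighted and takes line as a stratification factor. No text covers a control with a start date in both classes.

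Four other places bear on this.

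- SAP 5.1 admits a control only if the patient "has fulfilled the eligibility criteria for inclusion into the pooled external cohorts and has initiated chemotherapy". Every control therefore has a first line.
- SAP 6.2.1 makes the start of a later systemic therapy a primary-endpoint failure.
- SAP section 7, Table 2, splits controls into 34 first line and 8 second line or higher.
- The two subgroup analyses at the end of SAP 6.2.5 do state a control rule. The second-line subgroup takes controls who "take a second line of systemic therapy (for external historical cohorts) will be included in the analysis". The first-line subgroup takes controls with one line or more.

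Section 7 also gives the origin of exact matching. The SAP will "replace this sensitivity analysis for the choice of index date with the sensitivity analysis based on exact matching on the line of therapies", because otherwise "the analysis would have had an unbalanced sample size at N=32 versus 8".

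**The concern.** A control reaches a second line only after starting a further systemic therapy, and that start is itself a failure under the primary endpoint. For controls, Table 2 therefore records something that happens after the first-line index date. If each control is placed in one class by lines eventually received, the first-line stratum keeps only controls who did not fail in this way. The other 8 enter at second-line start, after their first-line failure, so that failure is counted in neither stratum. Larotrectinib patients are classed by the line at which they started the drug, which is fixed at their index date, so the selection falls on one arm only.

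What is at stake is how the sensitivity analyses are read. Protocol 9.7.6 and 9.9 rely on agreement between the main and sensitivity analyses, including on index date, to support the primary result. Under exclusive sorting, disagreement could come from the sorting and not from line of therapy.

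**Working it through.** **The plan's own figures.** SAP section 4 gives 51% power for 49 versus 42 patients, failure probabilities 0.04 and 0.19, and hazard ratio 0.25. With k = 49/42 = 1.167 and m = 49 × 0.04 + 42 × 0.19 = 9.94, power is Φ(√(1.167 × 9.94) × 0.75 / (1.167 × 0.25 + 1) − 1.96) = 50.7%, which agrees. Table 2 also reproduces: 34/42 = 81.0% and 8/42 = 19.0%. Its larotrectinib column sums to 19 + 32 = 51, against 49 in section 4; the control split is not touched by this.

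**Next-systemic-treatment failures in the first-line stratum** (documents only; intervals are exact 95%):

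| Rule | Failures | Share | Interval |
|---|---|---|---|
| All 42 controls from first-line start | 8/42 | 19.0% | 8.6–34.1% |
| Sorted as in Table 2 | 0/34 | 0% | 0–10.3% |

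**All failure types.** The documents do not give the share q of the 34 controls who fail by radiotherapy, mutilating surgery or death. Protocol 7.8 reports 2.9%, 6.9% and 5.2% for conventionally treated patients in general. These sum to 15.0% if they do not overlap, so I assume q from 0.05 to 0.15. Control failures are 8 + 34q with all 42 controls, and 34q with the 34 only:

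| q | All 42 | The 34 only |
|---|---|---|
| 0.05 | 9.7 (23.1%) | 1.7 (5%) |
| 0.10 | 11.4 (27.1%) | 3.4 (10%) |
| 0.15 | 13.1 (31.2%) | 5.1 (15%) |

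**Direction.** Suppose larotrectinib has no effect, so its first-line failure share equals the all-42 share. With exponential times, the hazard ratio (larotrectinib/control) against the 34 only is ln(1 − share) / ln(1 − q). This gives 5.1, 3.0 and 2.3 for q = 0.05, 0.10 and 0.15, where the true value is 1. A large-sample Cox simulation gave the same values to one decimal.

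**Pooled stratified estimate.** This was simulated at the Table 2 sizes: larotrectinib 19 and 32, exactly 8 of 42 controls starting a second line, true hazard ratio 0.25, exponential times, equal follow-up in each line, unweighted stratified Cox, 1,500 runs per scenario. The failure share p2 of controls in the later-line stratum is also an assumption. In the inclusive column the 8 appear in both strata. Entries are medians with the central 95% of estimates.

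| q | p2 | Exclusive sorting | All 42 in first line |
|---|---|---|---|
| 0.05 | 0.19 | 0.50 (0–4.41) | 0.24 (0–0.73) |
| 0.05 | 0.50 | 0.35 (0.09–1.44) | 0.25 (0.07–0.63) |
| 0.15 | 0.19 | 0.37 (0.04–1.64) | 0.24 (0.04–0.71) |
| 0.15 | 0.50 | 0.32 (0.09–1.03) | 0.25 (0.08–0.62) |

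Here q in effect applies to all 42 controls, so mean first-line control events under exclusive sorting are 2.1 and 6.3, slightly above 34q. A separate run of the same design gave medians within 0.03 of these. The tails are unstable in the sparsest scenario (q = 0.05, p2 = 0.19), where some runs have no finite estimate. Every exclusive-sorting range contains 0.25, so a single result would not reveal the bias.

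**The case against.** The strongest reply is that the SAP never adopts exclusive sorting. Table 2 stands in section 7 to explain why another analysis was dropped, not as a matching key. Indexing at the matched line can be read line by line, and then every control is available at first line. The remark about three or more therapies would justify pooling later lines under either reading, and the first-line subgroup beside it uses the inclusive rule. This stands, and it makes the bias conditional. It does not supply the missing rule: two programmers could build different datasets from the same text, and the only split on the page is the exclusive one.

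The study is also declared exploratory, this is one sensitivity analysis, and Protocol 9.7.6 says "Inconsistencies in the results will be explored through further analysis". That limits the weight of the point. Further exploration would, however, start from an estimate whose construction is unstated.

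A reader might infer four stronger things that the documents do not support.

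- **That the first-line stratum would have almost no control failures**, because 42 × 0.19 = 7.98 is close to 8. The 0.19 is a planning rate from a publication for any failure type, and other failures stay in the stratum.
- **That the bias can only hide a benefit.** The selection itself acts against larotrectinib, but the planned model is weighted and the weighted estimate was not examined.
- **That the SAP removed a warning attached to this same analysis.** Protocol 9.7.6 warns, for re-indexing controls at second line, that "it may fail to capture some clinically relevant events, for example control subjects receiving a second line of treatment". The analysis that SAP section 7 describes as replaced is the 32 versus 8 comparison of second-line patients. The caveat is similar in kind, and exact matching carries none.
- **That elapsed time is wrongly dated for re-indexed controls.** SAP 4.5 and 6.1.4 date to first-line chemotherapy, but the covariate wording in 6.2.5 refers only to initiation of treatment. A clarifying word is enough.

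**Conclusion.** The allocation rule is missing; that part holds without conditions. The bias holds if controls are sorted as in Table 2. The first-line controls are then selected on the absence of an endpoint event, and 8 of 42 next-systemic-treatment failures become 0 of 34. The first-line and pooled stratified estimates shift against larotrectinib, illustratively to a median pooled hazard ratio of about 0.3 to 0.5 when the truth is 0.25. That size rests on assumed values of q and p2, exponential times and no weighting, so only the direction and rough order should be relied on. The primary analysis and the first-line subgroup are unaffected. This should be corrected before the analysis is run, but it does not threaten the main result.

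**What to change.** State the allocation rule in SAP 6.2.5:

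- Enter all 42 controls in the first-line stratum, indexed at first-line start, with a second line counted as an event. The first-line subgroup wording already implies this.
- Enter the 8 again in the later-line stratum, indexed at second-line start, with age and elapsed time measured to that date.
- Keep the line-stratified model and log-rank test. Bootstrap by patient, not by record, and refit the propensity model in each resample, because there are 42 + 8 = 50 control records from 42 patients.
- Report control events by type in each stratum.

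The cost is SAP wording and patient-level resampling for one analysis, with no new data. The downsides are that 8 patients contribute correlated records, which also enter the propensity model and the stabilising probability, and that the later-line stratum still has only 8 controls. If exclusive sorting is intended, the SAP should say so and state that first-line failures leading to a second line are not captured.

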6.3 Analysis of Secondary and Exploratory Variable(s)

The following time-to-event secondary endpoints, [sections 6.3.1](#) to [6.3.8](#), will be analyzed using the steps outlined above, and incorporating the IPTW weights calculated for the primary endpoint. The sensitivity analyses detailed in [section 6.2.5](#) will be limited to the primary endpoint.

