A second pooled analysis was performed on 159 patients with *NTRK* gene fusion from the same 3 clinical trials *at data cut-off date of February 19, 2019* ([Hong 2020](#)) second analysis confirmed the results of the first one, with a best ORR of 79% (95% CI, 72-85), 16% of CR, 63% of PR and 12% of SD (investigator assessment), regardless of the type of tumors, the population (adult or pediatric) and the type of gene fusion involved. The median Duration of Response (DoR) was 35.2 months, the median progression-free survival (PFS) was 28.3 months and the median overall survival (OS) was 44.4 months. In the IFS population (n=28), 27 patients had an objective response (ORR 96%, 95% CI 82-100). The median duration of response was not estimable.

Moreover, the interim clinical study report of the SCOUT study, at data cut-off date of July 15, 2019, reported 88 patients of whom 38 patients were in the Phase I portion of the study (24 in escalation and 14 in expansion) and 50 patients were in Phase II. The full analysis set included all 88 treated patients. At the time of this interim analysis, all 79 *NTRK* gene fusion patients and all 9 of the non-*NTRK* gene fusion patients were evaluable for response. Within the *NTRK* gene fusion subgroup (consisting

⁶ Following a protocol amendment of the NAVIGATE study, the study now only includes patients older than 18 years.

predominantly of IFS and STS), 54 of the 79 patients with measurable disease had a confirmed objective response, yielding an ORR of 77% (95% CI: 66, 86) based on Investigator assessment. This included 21 CRs and 37 PRs (including 4 pending confirmation of a PR). Within the non-*NTRK* gene fusion subgroup, no responses were observed.

In the IFS population (n=34), the ORR was 94% (95% CI 80, 99). Among the patients with IFS, included in SCOUT at data cut-off of July, 2019, 21 patients had no other curative options besides disfiguring surgery or amputation before larotrectinib initiation. At the time of analysis, all of these patients showed responses, with 4 complete surgical responses, 7 complete responses and 9 partial responses recorded. None of these patients required an amputation or disfiguring surgery and no death was reported at the time of analysis.

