survived with major functional deficits or had mutilating surgery. In this series, almost 17% of patients may have experienced significant negative long-term effects with conventional therapies (20 patients treated with mutilating surgery and 5 with radiotherapy). In addition, 10 patients died mostly as a consequence of a tumor which was refractory to multiple lines of therapy. Altogether, these observations evidence that conventional conservative strategies demonstrate efficacy in IFS, even for the extensive tumors, but they are associated with acute and chronic side effects ([Orbach 2020](#), see [Section 7.4](#)).

To increase the robustness of the comparison for the primary analysis, events that are considered the most relevant in view of the multidisciplinary management of these tumor types will be selected. Chemotherapy is an essential component of the multimodality treatment with multiple lines considered in case of suboptimal outcomes, while surgery and radiation therapy acting as a local control may be associated with significant morbidities, with, in the worst case, failing to preserve the affected organ, particularly in the extremities. Three European studies analyzing the total burden of therapy for patients with IFS treated with conventional treatments showed that radiotherapy was used in 2.9% of patients, mutilating surgery was performed in 6.9% of patients and 5.2% of patients died of disease. Moreover, in main recent large series published in IFS, mutilating surgery, radiotherapy, alkylating chemotherapy and anthracycline agents were performed or used in 6-13%, 2-20%, 20-87% and 0-13% of cases, respectively ([Orbach 2020](#)).

The systemic treatment administered to the patient population targeted in this observational study is expected to either allow a complete response or to qualify the patient for non-mutilating complete surgical resection. Based on the experience of the experts of the field, tumor responses after conventional chemotherapy generally occur slowly over several months, whereas larotrectinib may lead to an early response (median time to response 1.8 months, with clinical improvement noted within days to weeks), which may be more important when there are life-threatening symptoms including tumor bleeding or organ compression. In cases of refractory tumors, life-threatening complications, or of metastatic tumors, TRKI should be immediately considered ([Orbach 2020](#)).

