9.7.5 Sample size and power considerations

The number of patients available is quite small, and no formal hypothesis and power calculations are considered for this study.

We can calculate the power for the comparison of two groups under a Cox Proportional Hazards Model, with the following applicable formula (Rosner 2006):

$$\text{Power} = \Phi \left(\frac{\sqrt{km}|\text{IRR}-1|}{k \times \text{IRR}+1} - z_{1-\alpha/2} \right)$$

where $m = \text{expected total number of events over both groups}$
 $= n_1 p_E + n_2 p_C$

$n_1, n_2 = \text{number of participants in experimental (E) and control (C) groups}$
 $k = n_1/n_2$ (ratio of participants in E versus C groups)

p_C = probability of failure in group C over time period of study

p_E = probability of failure in group E over time period of study

[figure not shown]
IRR = underlying hazard ratio

$z_{1-\alpha/2}$ is the $100(1-\alpha/2)$ -th percentile of the standard normal distribution

Φ is the CDF of $N(0,1)$

We assume 35 IFS subjects and probabilities of failure equal to 0.04 and 0.19 in SCOUT and the external historical control cohort(s), respectively. Even with a strong treatment effect (hazard ratio=0.25), the power can only reach 49%, as further additions to the control cohort lead to smaller increases in power as the two groups become increasingly unbalanced. Of note, an effect size of 0.5 would already be considered as a valuable treatment effect (Fewell 2007). Therefore, having a powered study seems unfeasible.

Figure 1: Representation of the study power in function of the number of patients included in the comparator arm (control) for different hazard ratios

$nE=35$ (number of patients in the experimental group (treated with larotrectinib))

$pE=0.04$ (probability of failure in the experimental group during the study)

$pC=0.19$ (probability of failure in the control group during the study) (Orbach 2020)

$RR=0.5$ to 0.2 (risk ratio)

$\alpha=0.05$ (type 1 error)

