As of the 20 July 2021 cut-off, there are 49 SCOUT IFS patients available for analysis. The pooled external cohorts from Curie and CWS will comprise N=42. Therefore, the power calculations in the protocol can be updated with current information on sample size as follows:

- N=49 IFS patients for SCOUT
- N=42 for pooled external control cohorts
- pE=0.04 (probability of failure in SCOUT) and pC=0.19 (probability of failure in control) per protocol assumptions
- Optimistic scenario of a strong treatment effect (HR=0.25)
- Power=51%
- Power cannot exceed 62.9% for N=49 for SCOUT and an unlimited number of subjects in the external arm

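### The weighted Cox hazard ratio planned for mutilating surgery, radiotherapy and overall survival will often not be estimable at the protocol's own event rates, and the SAP has no rule for an arm without events

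*SAP*

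**What the plan says.** SAP 6.3 states that the time-to-event secondary endpoints "will be analyzed using the steps outlined above, and incorporating the IPTW weights calculated for the primary endpoint". For mutilating surgery (6.3.2), radiotherapy (6.3.3) and overall survival (6.3.5), the steps carried over are those of SAP 6.2.4:

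- Kaplan-Meier curves with the median and quartiles;
- ordinary and weighted log-rank tests;
- an IPTW-weighted Cox HR, with a 95% interval of plus or minus 1.96 times the standard deviation of about 200 bootstrap log-HRs.

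The sample sizes in SAP section 4 are "N=49 IFS patients for SCOUT" and "N=42 for pooled external control cohorts". The planning rates for the composite are "pE=0.04 (probability of failure in SCOUT) and pC=0.19 (probability of failure in control) per protocol assumptions", with HR 0.25 as the optimistic case. Protocol 9.7.5 adds that "an effect size of 0.5 would already be considered as a valuable treatment effect".

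For the single components, protocol 7.8 reports that under conventional treatment "radiotherapy was used in 2.9% of patients, mutilating surgery was performed in 6.9% of patients and 5.2% of patients died of disease". It also cites wider ranges from larger series: 6-13% for mutilating surgery and 2-20% for radiotherapy. Protocol 7.2 gives 5-10% for death.

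Neither document gives expected events per component, a rule for an arm with no event, or a rule for bootstrap samples in which an arm has none.

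**The concern.** If one arm has no event, the partial likelihood has no finite maximum. The Cox HR is then zero or infinite, and the number printed depends on where the software stops iterating. Weighting cannot help, because it creates no events in an empty arm. This differs from low power, which yields a wide interval around an estimate that exists.

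Comparing these outcomes is a stated secondary objective. The HR is the only between-arm effect size the SAP plans for them, and it is most likely to fail when larotrectinib does well. Without a rule written beforehand, the replacement method would be chosen after the data are seen.

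**Working it through.** **Check on the inputs.** The documents' power formula with k = 49/42 and m = 49×0.04 + 42×0.19 = 9.94 gives Φ(√(k·m)·0.75/(k·0.25+1) − 1.96) = Φ(1.977 − 1.960) = 50.7%. SAP section 4 states 51%, so sample sizes, rates and HR are read as intended.

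**Expected events.** Control: 42·pC. Larotrectinib: 49·pE, with pE = 1 − (1 − pC)^HR.

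**Chance of no finite HR.** With a = (1 − pE)^49 and b = (1 − pC)^42, the chance that at least one arm is empty is a + b − a·b. For mutilating surgery at HR 0.25: pE = 1 − 0.931^0.25 = 0.0177, a = 0.417, b = 0.050, and a + b − a·b = 0.445 (0.4455 before rounding).

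| Endpoint (pC) | Control events | Larotrectinib events, HR 0.25 / 0.5 | Larotrectinib arm empty, HR 0.25 / 0.5 | No finite HR, HR 0.25 / 0.5 |
|---|---|---|---|---|
| Mutilating surgery (6.9%) | 2.90 | 0.87 / 1.72 | 42% / 17% | 45% / 21% |
| Radiotherapy (2.9%) | 1.22 | 0.36 / 0.72 | 70% / 49% | 79% / 64% |
| Death (5.2%) | 2.18 | 0.65 / 1.29 | 52% / 27% | 57% / 35% |

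**Wider ranges in the documents, HR 0.25.**

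- Mutilating surgery 6-13%: 2.5 to 5.5 control events; no finite HR 51% down to 18%.
- Radiotherapy 2-20%: 0.8 to 8.4 control events; 87% down to 7%.
- Death 5-10%: 2.1 to 4.2 control events; 59% down to 28%.

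The 20% figure for radiotherapy alone exceeds the plan's composite pC of 0.19, so that end of the range does not fit the planning assumptions. The plan's pE allows 49×0.04 = 1.96 larotrectinib patients with any composite event, shared over four components.

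**Bootstrap.** When an arm has a single event, a resample of that arm misses it with probability (1 − 1/49)^49 = 36%; with two events, (1 − 2/49)^49 = 13%. The log-HR is infinite in those resamples, so the standard deviation is unreliable even when the point estimate exists.

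**What the other steps leave.** SAP 6.2.4 reports only the median and quartiles. With at most 20% of controls expected to have any one of these events, even the first quartile is not expected to be reached. Protocol 9.7.4 promised survival probabilities at fixed times (6 and 12 months as examples) for all time-to-event endpoints, but SAP 6.2.4 does not carry them over. The log-rank test is defined with an empty arm. With x control events and none on larotrectinib, z is about 1.08·√x, so four control events are needed for p < 0.05. That has probability 33% (surgery), 3% (radiotherapy) and 17% (death) at the point rates.

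**The case against.** The strongest objection is to the rates. The 6.9%, 2.9% and 5.2% describe all conventionally treated patients, whereas controls here have locally advanced or metastatic disease and received chemotherapy. In protocol 7.8, 65 of the 172 patients are survivors treated by surgery alone, which leaves 107. All 10 deaths fall among those 107 (9.3%), and the chance of no finite HR for death at HR 0.25 drops to 31%. Radiotherapy at 5/107 (counted among survivors) drops to 62%. This stands, and is why a range is given. The chance remains too large to leave without a rule.

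A reader might also infer that an empty larotrectinib arm is the expected result, because of 21 high-risk SCOUT patients protocol 7.5.1 says "None of these patients required an amputation or disfiguring surgery and no death was reported at the time of analysis". The documents do not support that for every endpoint. For mutilating surgery the chance is 42% at HR 0.25 and 17% at HR 0.5. Zero of 21 has an exact two-sided 95% upper limit of 1 − 0.025^(1/21) = 16%, and the statement does not cover radiotherapy.

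A reader might further infer that the secondary objective would go unanswered. That is too strong: curves and log-rank tests remain, and protocol 9.7.4 already calls for probabilities at fixed times.

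Finally, the plan acknowledges rare events, sets no formal hypothesis and calls its results exploratory. That excuses low power. It does not tell the programmer what to print when the estimate does not exist.

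**Conclusion.** The concern holds for mutilating surgery, radiotherapy and overall survival. At the protocol's point rates the planned HR has no finite value with probability 45%, 79% and 57% if the true HR is 0.25, and 21%, 64% and 35% if it is 0.5. The documents' wider ranges at HR 0.25 give 18-51%, 7-87% and 28-59%. When the HR does exist, its bootstrap interval is unreliable with one or two events in an arm.

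The calculation assumes binomial event counts in 49 and 42 patients, proportional hazards, and published rates that apply to these controls. If the controls' rates are higher, as their disease stage and chemotherapy suggest, the lower parts of the ranges are more relevant. The point does not extend to time to subsequent systemic treatment or time to complete resection. It shows a fragile effect measure with no fallback, not a comparison that cannot be made.

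**What to change.** In SAP 6.3.2, 6.3.3 and 6.3.5:

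- **Counts and risks.** Report event counts per arm. Restore Kaplan-Meier cumulative incidence at fixed times (12 and 24 months), weighted and unweighted, with the between-arm difference.
- **Intervals.** For the unweighted results, name intervals that allow for censoring and stay finite at zero events, such as exact Poisson limits on events per person-time or a beta-product interval for the Kaplan-Meier estimate. Plain binomial limits will not do: SAP section 4 admits first doses up to the data cut-off of 20 July 2021, so some patients cannot have 12 months of follow-up. State that the weighted difference is descriptive when an arm has no event.
- **Hazard ratio.** When an arm has no event, print the Cox HR as not estimable, or give a Firth-penalised HR with a profile-likelihood interval. Report how many bootstrap samples had an empty arm.

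A minimum count such as five events per arm is not a good substitute. At the point rates and HR 0.25, the chance of five or more larotrectinib events is below 0.2% for each endpoint, so such a rule would in effect delete the HR.

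The cost is SAP wording and a few extra table columns. Some of these endpoints will have no ordinary HR to show beside the primary one.
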